N-Acetylcysteine for Youth Cannabis Use Disorder

Study Protocol

NCT0305537

Most recent IRB-approved protocol dated April 14, 2022

PROTOCOL TITLE: N-Acetylcysteine for Youth Cannabis Use Disorder**PRINCIPAL INVESTIGATOR: [name].****OBJECTIVES/SPECIFIC AIMS**

Cannabis use is particularly prevalent and problematic among youth, who are more likely than adults to initiate cannabis use, develop cannabis use disorder (CUD), and suffer lasting adverse cannabis-related consequences. Despite the clear need for youth-targeted cannabis cessation treatments, established modalities offer limited efficacy, with very few youth achieving sustained cannabis abstinence.

Among the most promising emerging youth-targeted cannabis cessation treatments is the over-the-counter antioxidant medication *N*-acetylcysteine (NAC). Our team previously demonstrated superior NAC versus placebo (PBO) abstinence outcomes in youth with CUD who concurrently received the behavioral treatment contingency management (CM). In order to optimally translate NAC to real-world clinical practice, further work is now needed to evaluate if NAC is efficacious independent of CM.

We propose a 12-week randomized placebo-controlled trial of NAC for CUD in youth ($N=192$). Participants will be randomized to double-blind NAC or PBO, yielding two equally-allocated treatment groups. All participants will receive brief weekly cannabis cessation counseling and medication management. The primary efficacy outcome will be the proportion of negative urine cannabinoid tests during the 12-week active treatment, compared between groups. We will also assess cognitive task performance at baseline, during treatment, and after treatment, examining changes in performance among participants who achieve abstinence versus those that do not.

- *Specific Aim 1.* Compare the effect of NAC versus PBO, added to brief weekly cessation counseling and medication management, on cannabis cessation in youth with CUD.
 - Hypothesis 1: NAC participants will have a higher proportion of negative urine cannabinoid tests during treatment than PBO participants.
- *Specific Aim 2.* Examine the impact of cannabis cessation on cognitive task performance.
 - Hypothesis 3: Participants who achieve abstinence will demonstrate significant improvement in attention, processing speed, verbal declarative memory, and cognitive control, compared to those who continue to use cannabis.

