The primary study hypothesis was that participants randomized to NAC would have higher odds than those randomized to placebo to submit negative weekly urine cannabinoid tests (UCTs) during treatment. An intent-to-treat (ITT) approach including all randomized participants was used. In all analyses, participants lost to follow up or absent for visits were coded as having a positive UCT at every missed visit.

The proportion of negative UCTs in the NAC and PBO groups at each visit (ITT sample) is shown in the adjoining figure. Though there was no group difference in baseline years of cannabis use, this variable was an independent predictor of positive UCT during treatment ($p=0.007$) and was therefore covaried in the model. Participants randomized to NAC had more than double the odds of negative UCTs during treatment, compared with those randomized to PBO. In the adjusted model, the relationship between treatment and the odds of a negative UCT was $OR=2.4$ (95% CI: 1.1-5.4), $p=0.021$. Through the final treatment visit, 40.9% (190/464) of the UCTs among participants in the NAC group were negative, compared to 27.2%

(126/464) among those in the PBO group, per ITT analysis, assuming any missing urine was positive for cannabinoids. At the post-treatment follow-up visit (four weeks after medication discontinuation), 19.0% (11/58) of the UCTs among participants in the NAC group were negative, compared to 10.3% (6/58) among those in the PBO group. While still numerically favoring NAC, the overall treatment effect lost statistical significance at post-treatment follow-up ($OR=2.2$ [95% CI: 0.7-6.5], $p=0.155$), though the trial was not powered for this outcome.

Models were examined for the possibility of confounding and effect modification of age, weight, gender, and number of previous cannabis quit attempts. None of the variables tested were significant confounders or effect modifiers (all $p>0.60$).

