This study is powered on the hypothesis that there is a clinically significant difference in proportions of negative urine cannabinoid tests (UCTs) among participants receiving NAC versus PBO.

Our previous findings demonstrated proportions of negative UCTs of 41% with NAC+CM and 27% with PBO+CM, but given that CM is itself a powerful treatment, we anticipate more modest proportions without a CM platform (62). Based on our other prior work using pharmacotherapy without a CM platform, we anticipate the proportion of negative UCTs in the PBO group will be between 6% and 10% (61). Although we have no prior clinical results for estimates of the efficacy of NAC alone, we anticipate that it will be at least as efficacious as CM in the proportion of negative UCTs (~27%), resulting in an overall anticipated effect of NAC versus PBO of 25% vs. 10%. With 12 weekly observations taken on each participant, a conservatively estimated autocorrelation as high as $p=0.90$, and a first order autoregressive covariance pattern, we will have greater than 80% power with two-sided $\alpha=0.05$ to detect the stated difference of 15% in proportions of negative UCTs with 67 participants per treatment group ($n=134$ total). Based on performance of past studies, we anticipate a 30% attrition rate during the study treatment period. The inflated samples size of 96 randomized participants per group ($N=192$ total) will thus provide superior power to detect the stated difference in the main effect of NAC versus placebo in the presence of up to a 30% attrition rate.

Based on our previous research we anticipate approximately 25% percent of participants will have negative UCTs at cognitive task performance assessment visits (23). Similarly, our data indicate that negative UCTs were associated with increased verbal memory and psychomotor speed scores at both 4 and 8 weeks during a cannabis cessation trial using NAC + CM versus CM alone (Cohen's $d=0.90$ and $d=0.60$; respectively). The randomized sample size of $N=192$ will provide superior power (99% and 82%, respectively) with an adjusted $\alpha=0.01$, to detect similar effect sizes across cognitive outcome measures taken at mid-treatment, end-of-treatment, and post-treatment follow-up.

Statistical Analysis

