Categorical clinical and demographic variables will be assessed by chi-square tests of independence, while continuous variables will be assessed using Student's t -test. In addition to baseline group differences, preliminary analysis of baseline characteristics with cannabis use outcomes of interest will examine significant correlates of abstinence in the study population. Characteristics found to be significantly associated with cannabis use outcomes will be included as covariates in the initial stages of model development. The primary measure of interest will be the proportion of self-reported abstinence confirmed with negative weekly UCTs (< 50 ng/mL) during the 12 weeks of active treatment. The main effect of NAC on negative weekly UCTs will be assessed with a repeated measure logistic regression using a general estimating equations framework (GEE) (126). Models will be computed both unadjusted and adjusted for significant covariates and confounders found in the preliminary analysis. Working correlation structures will be independently compared using the quasi-likelihood under the independence model criterion statistic (127). All randomized participants will be included in the primary analysis (intent-to-treat; ITT) and participants will be deemed non-abstinent at any missed visit (drop-out/loss-to-follow up included). Model based means will be used to construct the pairwise comparisons of groups (NAC versus PBO). In addition to the longitudinal analysis of negative UCT rates during treatment, rates will be compared between treatment groups at each post-treatment follow-up visit using logistic regression models. Similarly, creatinine adjusted cannabinoid levels will be examined between groups over the course of the treatment and at the post-treatment follow-up visits using linear mixed effects models. We will also, in exploratory fashion, examine group differences in other cannabis-related outcomes (e.g., self-reported cannabis use [Timeline Follow-Back], craving [Marijuana Craving Questionnaire], withdrawal [Cannabis Withdrawal Scale], and associated problems [Marijuana Problem Scale]). In distinct models, the effect of co-occurring tobacco use disorder on cannabis cessation outcomes will be examined. The main effect of co-occurring tobacco use

disorder, as well as the interaction between tobacco use disorder and each treatment assignment (NAC and CM), will be added to the primary efficacy model.

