Cognitive task performance will be assessed at pre-treatment, mid-treatment, end-of-treatment, and post-treatment follow-up. Task performance at the post-baseline time points will be compared between those who have and have not achieved abstinence at that time points using generalized linear mixed models with outcome appropriate distributions (Gaussian, Poisson, etc.). In addition to a binary indicator of UCT at each cognitive task measure visit, duration of abstinence will be examined as a predictor of cognitive performance. In exploratory fashion, we will also assess potential NAC versus PBO effects on cognitive task performance, as NAC possesses potential cognitive enhancing properties (128).

All analysis will be conducted using SAS version 9.4 (SAS Institute, Cary, NC, USA).

Missing Data and Attrition

Missing data in longitudinal studies can be a very problematic feature but can be mitigated through study design considerations. Attrition may introduce bias in the treatment group parameter estimate and reduce power, precision, and generalizability. In order to minimize missing data and study attrition, study simplification and enhanced communication between study coordinators and participants will be emphasized. We will make every effort to prevent attrition, e.g., telephone/text/e-mail reminders prior to visits, meeting with participants in community if needed, and reinforcing attendance at each visit. However, these methods do not ensure that all data will be collected and appropriate analysis methods will be employed to accommodate missing data. Mixed-effects models yield valid inferences assuming ignorable attrition (i.e., attrition is accounted for by covariates or the dependent variable measured prior to dropout). We propose a sensitivity strategy to examine the ignorability assumption. A pattern mixture model will be used to examine treatment response among participants with various dropout patterns and will be implemented in the mixed-effects framework (129-131) in which participants are classified by attrition pattern (e.g., early dropout, middle dropout, late dropout, completer). In addition, in keeping with the ITT Principle, we will make every effort to continue assessments for the entire course of randomized treatment, even among those who fail to adhere to randomized assignment or stop participating in the study assigned intervention.

C3g. Clinical Management Issues

Subject Discontinuation/Stopping Rules

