4.1 Summary of the Protocol

This application proposes a randomized controlled trial ($N=192$) of *N*-acetylcysteine for youth cannabis use disorder. Treatment-seeking youth with cannabis use disorder will be recruited from the local community, and enrolled participants will be randomized to receive a 12-week course of *N*-acetylcysteine or placebo, added to weekly cannabis cessation counseling and medication management. The primary efficacy outcome of interest is the proportion of negative urine cannabinoid tests during treatment, compared by treatment group. Cognitive task performance will be assessed prior to, during, and after treatment, to investigate whether participants achieving abstinence exhibit cognitive task performance improvement relative to participants who do not achieve abstinence. Inclusion and exclusion criteria are outlined above. Power and sample size calculations are in Section C3f.

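### Aim 2 asks about cognitive improvement, but the analysis sentence compares post-baseline scores by observed abstinence and does not specify a role for the week-0 score

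*Combined protocol and SAP*

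**What the plan says.** The objectives describe the cognitive work as "examining changes in performance among participants who achieve abstinence versus those that do not". The hypothesis under Specific Aim 2 is that "Participants who achieve abstinence will demonstrate significant improvement in attention, processing speed, verbal declarative memory, and cognitive control", relative to those who keep using. Section 4.1 gives the purpose as "to investigate whether participants achieving abstinence exhibit cognitive task performance improvement relative to participants who do not achieve abstinence".

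A usable baseline is collected. Under C3e the screening session is for training and practice, and the Study Timetable places the battery at week 0 and at three later points (mid-treatment, end of treatment, last follow-up).

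The Aim 2 analysis text in C3f lists the pre-treatment assessment in the series, then says: "Task performance at the post-baseline time points will be compared between those who have and have not achieved abstinence at that time points". The model family is the generalized linear mixed model. Abstinence enters as urine cannabinoid test (UCT) status at each cognitive visit and, additionally, as duration of abstinence. No baseline covariate, change score or time-by-abstinence term is named.

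The nearest covariate rule stands earlier in the same section: "Characteristics found to be significantly associated with cannabis use outcomes will be included as covariates in the initial stages of model development".

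**The concern.** Improvement is a statement about two time points; the written contrast uses only the later ones. Randomization does not protect that contrast, because participants sort themselves into abstinent and non-abstinent after allocation.

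The documents make a prior difference plausible without measuring it. C1a reports of the earlier youth trial: "Though there was no group difference in baseline years of cannabis use, this variable was an independent predictor of positive UCT during treatment" (p=0.007). Section A describes a dose-dependent link between adolescent use and poorer cognition. Together these suggest that those who later abstain could have scored better at the start.

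The covariate rule does not clearly close the gap. It is keyed to cannabis-use outcomes, it depends on a significance test, and nothing says that it extends to the cognitive models or that week-0 cognition is among the characteristics screened.

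At stake is whether an Aim 2 finding can be read as recovery. The background section presents that aim as informative whatever the efficacy result, so it has to stand on its own.

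**Working it through.** **Inputs from the documents (C3f, Power and Sample Size).** N=192; "approximately 25% percent of participants will have negative UCTs at cognitive task performance assessment visits", so 48 versus 144; planning effects d=0.90 and d=0.60; adjusted alpha 0.01; stated power 99% and 82%.

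**Assumptions not in the documents.** Two-sided test; size of the prior gap; correlation ρ between week-0 and later scores (the ICC in the mixed model); persistence of UCT status across visits.

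**1. The plan's own power.** For an unpaired two-group t-test with SD 1, the standard error is √(1/48 + 1/144) = √(4/144) = 1/6, so the noncentrality is 6d: 5.4 and 3.6. Power is 99.7% and 84.0%, within 2 points of the stated 99% and 82%. The stated power therefore fits a simple comparison with no gain from a baseline score.

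**2. What leaks at one visit with no true recovery.** Let δ be the week-0 gap, abstainers higher.

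| Mechanism | Later score only | Adjusted for week 0 | Change from week 0 |
|---|---|---|---|
| Stable gap that persists | δ | (1−ρ)δ | 0 |
| Abstinence depends on the measured week-0 score, so the gap regresses | ρδ | 0 | −(1−ρ)δ |

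With δ=0.3 and ρ=0.7, the first row gives 0.30 / 0.09 / 0 and the second 0.21 / 0 / −0.09. With ρ=0.5 the rows are 0.30 / 0.15 / 0 and 0.15 / 0 / −0.15. Adjustment reduces the bias in both rows; neither alternative removes it in both.

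In the stable case the single-visit noncentrality is 6 × 0.3 = 1.8, which is significant at 1% in 21.4% of trials. For δ=0.2 and 0.1 the rates are 8.3% and 2.5%.

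**3. What leaks in the planned mixed model.** A random-intercept model also uses people whose status changes between visits, and a stable gap does not affect that information, so the leak is smaller than in step 2. Simulation set-up: N=192, one week-0 and three later scores, total SD 1, 25% UCT-negative per visit, status correlation 0.7, stable gap defined as the difference by UCT status at a single visit, REML fit, two-sided alpha 0.01, no true effect. Ranges are over repeated simulations of this set-up.

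| Gap | ICC | Post-baseline only | Week-0 adjusted | Change |
|---|---|---|---|---|
| 0.1 SD | 0.7 or 0.5 | about 2% | – | – |
| 0.2 SD | 0.7 | 3.5% | 2.3% | 1.0% |
| 0.2 SD | 0.5 | 6.6-6.7% | 3.1-3.6% | 1.0-1.2% |
| 0.3 SD | 0.7 | 5.1-7.8% | 2.9-4.1% | 0.8-1.1% |
| 0.3 SD | 0.5 | 14.2-16.8% | 7.4-8.5% | 0.9% |

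At a 0.3 SD gap, the false effect in the post-baseline model is 0.07-0.13 SD (ICC 0.7) or 0.13-0.19 SD (ICC 0.5) over status correlations 0.5 to 0.9.

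**4. How far the assumptions move this (post-baseline model, status correlation 0.7).**
- A 0.3 SD gap between ever- and never-abstinent participants gives 5.1% (ICC 0.7) and 9.0% (ICC 0.5). If the gap scales with the share of abstinent visits, the rates are 2.8% and 6.6%.
- A 0.3 SD gap at ICC 0.3 gives 32.3% (19.1% after adjustment). A 0.4 SD gap at ICC 0.5 gives 33.9% (16.5%).
- With N=134 (30% attrition) and a 0.3 SD gap, the rates are 4.8% and 10.7% (2.7% and 5.3% after adjustment).

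**5. Power with no gap, true effect 0.3 SD, status correlation 0.7.**

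| ICC | Post-baseline only | Week-0 adjusted | Change |
|---|---|---|---|
| 0.7 | 88% | 95% | 93% |
| 0.5 | 72% | 80% | 72% |
| 0.3 | 65% | 69% | 53% |

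For the plan's d=0.60 at one visit, adjustment turns d into d/√(1−ρ²). At ρ=0.5 this is 0.60/0.866 = 0.69, and power goes from 84.0% to 93.9%.

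**The case against.** The strongest reply is that the sentence is a sketch. It names a contrast, its time points and a model family, but no covariates at all, so silence about week 0 is not exclusion. The preceding sentence lists the pre-treatment assessment, and the missing-data text contemplates covariates and earlier outcome values in mixed models. This stands: a reader might infer that the plan leaves the week-0 score out of the cognitive models, and the documents do not support that. They leave its role unspecified.

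Second, the covariate screen looks for correlates of abstinence, which is the Aim 2 exposure, and may have been meant generally. If week-0 cognition were screened at an assumed p<0.05, it would be selected in 60-62% of trials at a 0.3 SD gap. False positives would then be 2.7% (ICC 0.7) and 8.5% (ICC 0.5), against 2.9% and 8.5% for always adjusting. On that reading compulsory adjustment hardly changes the bias. It still gains power when there is no gap: 95.1% against 88.6% (ICC 0.7) and 80.0% against 72.7% (ICC 0.5). The text does not, however, establish that the screen applies. The baseline check in section 4.4 does not settle it either, since it concerns comparability across conditions.

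Third, the bias figures rest on assumed inputs and on how the gap is defined. That is correct, and it limits what can be claimed about size.

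**Conclusion.** The point holds as a gap between the stated aim and the written analysis. Aim 2 concerns improvement; the Aim 2 analysis text compares later scores by non-randomized status and secures no role for a baseline that the trial collects. The direction and mechanism of the possible bias can be shown; its size cannot be known from the documents. Under the set-up above, a 0.3 SD gap means roughly 5-8% or 14-17% false positives instead of 1%, and a 0.1 SD gap about 2%. Other definitions of the gap give smaller figures; a lower ICC or a larger gap gives larger ones. The gain in power from adjustment does not depend on any gap.

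Two stronger conclusions are not supported. A reader might infer that effects of the planned size could be produced by a prior difference alone, but the false effect at a 0.3 SD gap (0.07-0.19 SD) is far below d=0.60-0.90. A reader might also doubt the stated cognitive power, but it reproduces to within 2 points. The primary NAC versus placebo comparison is untouched. The change is worth making for a secondary, observational aim; confidence in the size is moderate at best.

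**What to change.** Add to the cognitive paragraph of C3f, in substance:

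> Every cognitive model includes the week-0 score of the same test as a covariate, whatever its significance; this gives the main Aim 2 estimate. The abstinence contrast in change from week 0 is reported as a named sensitivity analysis. For count outcomes, week 0 enters as a covariate only. The result is described as an observational association.

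Naming one main estimate matters because the two can disagree, and otherwise the hypothesis could be supported by whichever is favourable. Adjustment for age stratum, tobacco stratum and years of cannabis use is optional and separate from this point.

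The cost is one more analysis and a simple rule for missing week-0 scores; no new data are needed. The limits should be stated too. Baseline adjustment leaves part of a stable gap (7.4-8.5% false positives at 0.3 SD and ICC 0.5). Change from week 0 has less power than adjustment, falls below the post-baseline model at ICC 0.3 (53% against 65%), and is biased against recovery by gap × (1−ρ) if the gap regresses to a common mean: 0.3 × 0.3 = 0.09 SD at ρ=0.7 and 0.3 × 0.5 = 0.15 SD at ρ=0.5. Residual confounding remains under either analysis.

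### The Aim 2 comparison of cognition by abstinence has no treatment-arm term, so if NAC both raises abstinence and acts directly on cognition, part of the drug effect is counted as cessation

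*Combined protocol and SAP*

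**What the plan says.** Specific Aim 2 is to "Examine the impact of cannabis cessation on cognitive task performance". The Statistical Analysis part of C3f carries it out as follows: "Task performance at the post-baseline time points will be compared between those who have and have not achieved abstinence at that time points". Besides the urine-test indicator at each cognitive visit, it says that "duration of abstinence will be examined as a predictor of cognitive performance". No other predictor is named for these models.

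The same paragraph then adds: "In exploratory fashion, we will also assess potential NAC versus PBO effects on cognitive task performance", giving as its reason "as NAC possesses potential cognitive enhancing properties". C1c also describes this as exploratory. Neither place says that the drug comparison is made inside the Aim 2 model or used to adjust the abstinence contrast.

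The general covariate rule, earlier in Statistical Analysis, is that "preliminary analysis of baseline characteristics with cannabis use outcomes of interest will examine significant correlates of abstinence". It covers baseline characteristics and so does not bring in randomized arm. Where the plan does want extra terms it names them: co-occurring tobacco use disorder and its interaction with treatment are added to the efficacy model.

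Power and Sample Size plans on 25% negative urine tests with NAC and 10% with placebo. For Aim 2 it assumes about 25% of participants negative at the cognitive visits, d=0.90 and d=0.60, an adjusted alpha of 0.01, N=192, and power of 99% and 82%.

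**The concern.** Under the plan's own hypotheses, randomized arm is related to both sides of the Aim 2 comparison. NAC is expected to make abstinence more common, and NAC is said to have possible effects of its own on cognition. A factor that drives both exposure and outcome confounds a comparison that leaves it out.

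At weeks 6 and 12 participants are still taking study medication, so the drug effect would be concurrent. Adjusting for the pre-treatment cognitive score would not remove it. What is at stake is attribution: some of any direct NAC effect on test performance would be reported as recovery from stopping cannabis, and the share grows with the success of NAC on the primary outcome.

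**Working it through.** **Inputs.** From Power and Sample Size: 25% vs 10% negative tests; a placebo range of 6% to 10%; the prior youth trial's 41% vs 27%; 25% negative at cognitive visits; N=192; alpha 0.01 (two-sided assumed, since sidedness is not stated there); d=0.90 and 0.60. From the Randomization text: 1:1 allocation. Assumed: a direct NAC effect on cognition of δ = 0.2 to 0.5 SD.

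**1. The plan's own figure.** 25% of 192 is 48 abstinent and 144 not. A two-sample t-test has noncentrality d × √(48 × 144/192) = 6d, that is 5.4 and 3.6. Power is 99.7% and 84.0%, against 99% and 82% stated. The stated figures therefore correspond closely to a plain two-group comparison with no arm term.

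**2. Arm composition.** With 1:1 allocation, the NAC share is pN/(pN+pP) among the abstinent and (1−pN)/(2−pN−pP) among the others. At 25% vs 10% these are 25/35 and 75/165.

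**3. Bias.** The unadjusted contrast picks up gap × δ.

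| Negative tests, NAC vs placebo | NAC share, abstinent | NAC share, non-abstinent | Gap | Bias at δ=0.2 | Bias at δ=0.5 |
|---|---|---|---|---|---|
| 25% vs 10% | 71.4% | 45.5% | 26.0 points | 0.052 SD | 0.130 SD |
| 25% vs 6% | 80.6% | 44.4% | 36.3 points | 0.073 SD | 0.181 SD |
| 41% vs 27% | 60.3% | 44.7% | 15.6 points | 0.031 SD | 0.078 SD |
| Equal rates | 50% | 50% | 0 | 0 | 0 |

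At the planned rates the bias is 0.052/0.60 = 9% to 0.130/0.60 = 22% of d=0.60. A direct effect of 0.60/0.260 = 2.3 SD would be needed to produce d=0.60 alone.

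**4. Error rate with no true cessation effect.** Let P be the overall abstinent fraction and k = bias × √(192 × P(1−P)). The rejection rate is 1−Φ(2.576−k)+Φ(−2.576−k). Planned rates of 25% and 10% imply P = 17.5%, whereas the Aim 2 power statement uses 25%, so each case is worked with a matching composition.

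- P = 17.5% (25% vs 10%): √27.72 = 5.265; k = 0.27 and 0.68; error 1.3% and 3.0%.
- P = 25% with the same 2.5:1 ratio (35.7% vs 14.3%): gap 71.4 − 42.9, or 28.6 points before rounding the shares; √36 = 6; k = 0.34 and 0.86; error 1.45% and 4.3%.

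A simulation of a single visit (60,000 trials per setting) gave 1.3% and 2.8% in the first case and 1.4% and 4.0% in the second. With arm in the model the bias was 0.00 SD and the error about 1.0% throughout.

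**5. Cost of the arm term.** The variance of the abstinence coefficient rises by 1/(1−φ²), where φ is the correlation of arm with abstinence. At 25% vs 10%, φ = 0.20 and the factor is 1.04. At P = 25%, φ = 0.25 and the factor is 1.07; power becomes 99.5% (d=0.90) and 81.1% (d=0.60), from 99.7% and 84.0%.

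**The case against.** The bias needs two conditions, and neither is established. A reader might infer that the abstinent group will be mostly NAC participants. The documents do not support that as a fact: C1b reports that the adult trial (N=302) found no overall NAC effect, and Power and Sample Size says there are no prior clinical results for NAC alone. The cognitive effect is only called potential, and the supporting reference is, by its title, a study in rats. Both points stand, so the finding is conditional. They do not remove it, since an analysis should be sound under the hypothesis the trial was built to test.

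The plan does commit to a NAC versus placebo comparison on cognition, which would help show whether a drug effect exists. It does not adjust the abstinence contrast. Nor does the text exclude an arm term; it is a short description that does not mention one. The gap is an omission to close, not a stated decision to leave arm out.

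It is also tempting to read the opening section's remark, that the trial can examine cognition with abstinence whatever the efficacy result, as contradicted by the model. That remark is more naturally about feasibility and does not claim that the contrast is unaffected by arm.

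Finally, adjustment is not free. If NAC has no cognitive effect, arm predicts only abstinence, and including it slightly amplifies any remaining confounding, by roughly the same 4% to 7% as the variance factor.

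**Conclusion.** The concern holds in conditional form. As written, the Aim 2 models are confounded by treatment arm if NAC raises abstinence and also acts directly on cognition. Across the three non-zero scenarios the bias is about 0.03 to 0.18 SD for an assumed direct effect of 0.2 to 0.5 SD; if NAC does not change use, there is none.

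Two stronger readings are not supported. A drug effect could not on its own account for d=0.60 or d=0.90; the issue matters most for small differences across a battery of many tests. And adding arm would not isolate the effect of cessation: abstinence is self-selected, and differences in severity and motivation would remain. This is a worthwhile, inexpensive correction to a secondary, non-randomized aim. The missing term is clear from the text; the size of the consequence is not, because it rests on assumptions about NAC that the documents do not quantify.

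**What to change.** In the cognitive paragraph of Statistical Analysis (C3f), state that randomized arm enters every Aim 2 model as a fixed term, for both abstinence status and duration of abstinence, and that the arm-adjusted abstinence contrast is the Aim 2 result. The arm coefficient in that model should not be read as the total effect of NAC on cognition, because abstinence is held fixed.

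Read the already planned week 26 comparison as the off-drug check, about 14 weeks after treatment ends. Restrict it to true week 26 visits: under Post-Treatment Follow-Up, early-termination visits use the week 26 schedule and may fall during treatment.

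Describe the Aim 2 result as an association. No new data are needed. The cost is one degree of freedom and about 3 points of power at d=0.60 (84.0% to 81.1%), which puts it slightly under the stated 82%.
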